## **VI. Special precautions, including dose modifications**

We will not make modifications of the vitamin D dose based on the study design. As described in Section XI, "Monitoring Subject Safety", subjects will be advised to cease vitamin D supplementation if they experience adverse effects commensurate with hypercalcemia. Subjects will be asked to discontinue taking any non-doctor recommended supplements containing more than 1,000 IU of vitamin D when they begin taking study-provided supplements.

## **VII. Description of experimental controls and use of placebos:**

In this 2,000-person two-arm, double-blinded randomized controlled trial, we will randomize half the subjects to low dose vitamin D therapy (400 IU/day), which will serve as the control group, and half to a moderate (4,000 IU/day) dose. Participants will have the option of being randomized to the moderate versus low strategy. Transitional participants will maintain their dosing arm from the previous NIH study; those in the high or moderate dosing arms (10,000 IU/day or 4,000 IU/day) will receive 4,000 IU/day and those who were previously in the low arm (400 IU/day) will receive 400 IU/day. The low dose was selected to ensure that all subjects had a high likelihood of a total vitamin D intake that met the recommended daily allowance (RDA).

## **VIII. Type and number of experimental subjects:**

As noted, we plan to recruit 2,000 participants. Recruitment information will vary by partner, but recruitment materials and emails will have links to the research website for additional information and enrollment. On the website, interested participants will complete a 2-minute eligibility questionnaire to determine their eligibility for the study. Persons reporting health conditions indicating risk from vitamin D treatment (hypercalcemia, hyperparathyroidism, some medications, kidney stones, pregnancy, lactation) or an allergy to vitamin D will be ineligible.

*Individuals are eligible to enroll in the study if they:*

1. Are 18 years or older.

*Individuals are excluded from the study if they:*

1. Report being pregnant, planning to become pregnant, and/or report breastfeeding during the study period.
2. Report a history of chronic kidney disease, including a history of abnormal GFR and/or creatinine.
3. Report a history of hyperparathyroidism.
4. Report a history of increased falls.
5. Report a history of hypercalcemia.
6. Report a history of gastrointestinal absorptive disorders, including having undergone bariatric surgery.
7. Report a history of kidney stones (1 in past year or 2 in lifetime).
8. Report already taking more than 400 IU of vitamin D daily as recommended by a medical professional, and/or taking D2.
9. Report a history of sarcoidosis.
10. Report an allergy to vitamin D.
11. Are unwilling to take daily vitamin D.

Eligible participants will be guided to a secure REDCap website where they will complete a electronic consent form and a 15-minute baseline survey that asks about demographics, health and health behaviors (including vitamin D intake and sun exposure), and COVID-19 risks. For transitional participants from the NIH study, those who have recently completed the NIH study will not take a new baseline survey, as they will have recently completed a follow-up survey from the previous study that includes the same questions. These participants will be directed to a new consent form that includes eligibility criteria to be enrolled in this study. Participants that have graduated from the NIH study prior to the approval of this amendment (amendment #24 for #IRB20-0847), will be considered new participants and will complete the same eligibility screening, consent, and baseline survey process as other new participants.

As noted, we plan to recruit 20% (200 participants) of the eligible participants at the beginning of the study to receive and complete a self-guided, at-home vitamin D level and a COVID-19 anti-body test at their places of residence. At the end of the study, all study participants were to be offered an at-home COVID-19 antibody test kits. Please note that these tests were halted in early 2024. Participants will have the option to opt in or out of these tests on the study consent form. Participants who opt out of the at-home antibody test will still be able to participate in the study and receive Vitamin D supplements.

Participants will have the option to receive their vitamin D results and their antibody test results at the end of the study. If positive, communication of the antibody results will clearly indicate that there is evidence of past exposure to SARS Cov2 virus but that it is not known whether such indication is related to the presence or absence of immunity to future infections. To ensure only secure release of information, request for release of information will only be honored when communicated by email or text from the email address or cell phone number used to register the participant, and will be provided by mail only to the address registered by that individual upon enrollment.

During the 12-month implementation period, we will ask participants to complete online follow-up surveys every 3 months. The follow-up surveys at months 3, 6, and 9 will ask the participant whether they have had a

confirmed diagnosis of COVID-19, and the date if so, ask about rates of study medication adherence, and assess for changes in the intake questions about use of other supplements, sun exposure, diet, exercise, and COVID-19 exposures. If the patient is reported to have had COVID-19, we ask about severity, including hospitalization and duration, type of COVID-19 testing used, and need for mechanical ventilation and duration, and COVID-19 symptom severity using the BEAT-19 adapted to reflect the worst symptomology during their period of active COVID-19.

## **IX. Description of statistical analysis**

The higher doses we propose, 4,000 IU/d is expected to maximize the vitamin D treatment effect if one exists compared to a lower high dose as in a Harvard study currently underway which explores 2,000IU/day vitamin D. While the Harvard study gives vitamin D in the context of acute infection or household exposure so vitamin D levels may not respond quickly enough to affect outcomes (perhaps both for treatment and prevention), our proposed design seeks to raise vitamin D levels in advance of sustained risk in community members who are disproportionately at increased risk of COVID-19, increasing the underlying risk of COVID-19 that increases the expected treatment effect, and therefore increases overall statistical power.

For our primary outcome of COVID-19 infection as measured by patient report of clinically confirmed COVID-19 (or viral PCR when available) and secondary outcomes of COVID-19 antibody seroconversion and disease severity (hospitalization, ICU stay, ventilator use, death), hazard models will be employed to assess the effect of each vitamin D dosing strategy on the outcome. We will first develop hazard ratios for between-group analyses on the primary outcome using log-rank tests, and then develop Cox proportional hazard models to model the hazard function on a set of covariates including but not limited to vitamin D dose, baseline vitamin D levels, age, gender, race, ethnicity, sun exposure, sleep habits, exposure of cohabitants, job type, and study site. We will also control for randomization date to adjust the underlying hazard function for COVID-19 prevalence over time. As noted above, we estimate statistical power using a simulation model based on conservative estimates of the fraction of Chicagoans already immune but unaware they have had COVID-19 ( $\leq 10\%$ ), monthly incidence of COVID-19 (3%/month for Black/Latinx persons and 1%/month for White persons), size of the true effect of vitamin D on incidence we seek to assess, confidence we wish in that assessment, and length of time participants are followed. Based on this we propose to recruit at least 2,000 participants, yielding 80% power at  $p < 0.05$  to demonstrate a reduction of 20% or more in COVID-19 incidence due to vitamin D within 12 months of randomization.

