A minimum of 2,000 eligible participants will be randomized to the 400 IU/day or 4,000 IU/day treatment arms. Each lot of vitamin D supplements will be tested to ensure they are within the dosing tolerance that meets USP standards. Transitional participants will maintain their dosing arm from the previous NIH study; those in the high or moderate dosing arms (10,000 IU/day or 4,000 IU/day) will receive 4,000 IU/day and those who were previously in the low arm (400 IU/day) will receive 400 IU/day. The UCM pharmacy will prepare and package blind-label safety-top medication bottles to be distributed to participants via mail to either their home address or for pick-up from community partners. During the 12-month implementation period, we will ask participants to complete follow-up surveys every 3 months. A sample of the participants (20%) who complete the surveys also have the opportunity to receive a free home COVID-19 antibody blood spot test and Vitamin D level tests at the beginning of the study. Both tests are done at home by the participant themselves. Testing this subset will allow the research team to capture baseline levels of Vitamin D and immunity to COVID-19. We suspect 10% will have positive antibodies and 80-90% will be Vitamin D deficient; these baseline sample tests will confirm the general hypothesis. Originally, we planned for the entire sample to be offered the opportunity to receive a free, in home COVID-19 antibody blood spot tests at the end of the study. Due to low return rate, we paused end of study testing in early 2024 and now wish to permanently discontinue it. Over the course of this three year study, it is likely that most participants have COVID-19 antibodies, therefore testing is no longer scientifically valuable. Results of the antibody test will help inform research outcomes and may increase completion of quarterly self-reported surveys.

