Primary analysis: We will use a multivariable Cox proportional hazards regression model to estimate an adjusted hazard ratio of the effect of moderate versus low dose vitamin D on the outcome. Covariates will include age, sex, race and ethnicity, baseline sun exposure, baseline insomnia severity, baseline COVID-19 exposure outside work, baseline employment, randomization date, and baseline geographic location. The selection and coding of these covariates mirror a prior NIH-funded trial of vitamin D and COVID-19 (NCT04868903). Coding of these covariates include age (continuous), sex (male versus female), race and ethnicity (non-Hispanic White versus non-White or Hispanic), sun exposure (average \leq 30 minutes per day versus $>$ 30 minutes per day), insomnia severity (no or subthreshold insomnia versus moderate or severe insomnia), COVID-19 exposure outside work (no versus yes), and employment (no versus yes). Non-Hispanic White participants will be defined as those who report White race and non-Hispanic or Latino ethnicity. Non-White or Hispanic participants will be defined as those who report either non-White race or Hispanic or Latino ethnicity. Whereas recruitment in the NIH trial was limited to Chicagoland and stratified by recruitment site (UChicago Medicine and Rush University Medical Center), this study recruited participants across the United States, such that we will include baseline geographic location as a covariate, defined by baseline mailing address latitude $<$ 40.0 or \geq 40.0 degrees. Furthermore, whereas the NIH trial recruited participants who concluded their participation prior to when Omicron arrived in Chicago about December 1, 2021, every participant in this study could be active in the study after Omicron arrived in the United States about December 1, 2021. Rather than control for randomization date with a linear time trend and an indicator variable for potential participation after Omicron arrived like the NIH trial, we will control for randomization date with a series of thirteen quarters defined by calendar quarter and year (Q1 2021 [December 2020 through March 2021], Q2 2021 [April 2021 through June 2021], Q3 2021 [July 2021 through September 2021], Q4 2021 [October 2021 through December 2021], Q1 2022 [January 2022 through March 2022], etc. up to Q1 2024 [January 2024 through April 2024]).

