Treatment heterogeneity analysis: We will use a multivariable Cox proportional hazards regression model to estimate an adjusted hazard ratio of the effect of moderate versus low dose vitamin D on the outcome in every subgroup of participants defined by the covariates in the primary analysis, except for the thirteen quarters defined by calendar quarter and year. Age will be dichotomized as <45 or ≥ 45 years. We will also analyze subgroups of Blacks or African-Americans, non-Whites or Hispanics with baseline mailing address latitude ≥ 40.0 degrees, non-Whites or Hispanics with baseline mailing address latitude <40.0 degrees, non-Hispanic Whites with baseline mailing address latitude <40.0 degrees, participants unimmunized for COVID-19 at baseline, and participants fully immunized for COVID-19 at baseline. Full immunization refers to one vaccine dose from Johnson & Johnson or two vaccine doses from other manufacturers.

Additional outcomes: We will analyze COVID-19 infection severity for moderate versus low dose vitamin D as measured by rates of symptoms using a modified Beat COVID-19 instrument (NCT04337762), hospital admission, hospitalization with ICU admission, hospital length of stay, whether ventilator, high-flow nasal oxygen, or helmet-based ventilation is used, and death.

Other Statistical Considerations

Proportional Hazards Assumption: In the primary analysis, secondary analysis of non-Hispanic White participants living north of 40.0 degrees, time-varying analysis, and treatment heterogeneity analysis, the proportional hazards assumption will be assessed using the *estat phtest* command in Stata with rejection of proportion hazards defined by $p < 0.05$ for any variable or the global test, or by visual assessment of Schoenfeld residuals. Continuous variables which fail proportional hazards will be categorized. For any categorical variable or categorized continuous variable which fail proportional hazards, we will perform Cox regression which stratifies based on that variable. If the moderate dose vitamin D variable fails the proportional hazards assumption, we will estimate non-proportional hazards models.

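### The 80% power allows only for unrecognised past infection (at most 10%) as immunity at entry, although vaccinated and knowingly infected people can enrol until April 2024; restate it as a range

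*Protocol*

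**What the plan says.** Protocol sections III (closing power paragraph) and IX describe the same simulation. Its listed inputs are "conservative estimates of the fraction of Chicagoans already immune but unaware they have had COVID-19" (10% or less), a monthly incidence of 3% for Black and Latinx and 1% for White participants, the effect size, the confidence sought and the length of follow-up. Section IX continues: "Based on this we propose to recruit at least 2,000 participants", for 80% power at p < 0.05 to show a 20% reduction within 12 months. Neither vaccination nor recognised past infection is among the inputs. The SAP contains no power calculation.

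On who can enter:

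- Protocol section VIII has age 18 or older as its only inclusion criterion. The list opening "Individuals are excluded from the study if they" has eleven entries, and none concerns past COVID-19 or vaccination.
- The SAP's treatment heterogeneity analysis includes "participants fully immunized for COVID-19 at baseline" as a subgroup.
- The SAP's primary analysis adjusts for randomization quarter from December 2020 "up to Q1 2024 [January 2024 through April 2024", and says recruitment was nationwide.

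On antibodies, section III says of baseline testing: "We suspect 10% will have positive antibodies". Sections III and V, explaining why end-of-study testing was dropped, say that over the three-year study "it is likely that most participants have COVID-19 antibodies".

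**The concern.** For a power calculation, a conservative immunity input is one that overstates the share of participants not at risk. A bound restricted to unrecognised infection does the opposite once vaccinated people and people with a known infection are also randomized. The protocol's background section still describes a widespread vaccine as possibly a year or more away, which places the power text before vaccination. The input was reasonable for that setting, but neither document revisits it for people randomized in 2022 to 2024 or outside Chicago.

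Expected events scale with the share still at risk at entry, and power follows events. If the trial finds no effect, the 80% is the figure a reader will use to decide how strongly the result speaks against a 20% reduction. If it describes a more susceptible population than the one enrolled, a null result will be over-read.

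**Working it through.** **Inputs.** 2,000 participants, 1:1 (Protocol section VII: "we will randomize half the subjects to low dose vitamin D therapy (400 IU/day), which will serve as the control group"); 20% reduction over 12 months; 3% and 1% per month; 10% immune; p < 0.05. Not stated: test sidedness, racial mix, and whether the 20% is a hazard ratio or a ratio of 12-month risks. Two-sided testing, complete follow-up and full immunity of the immune share are assumed below.

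**Step 1: the plan's own 80%.** It cannot be reproduced uniquely, but some readings reach it. With linear accumulation and 75% Black/Latinx, the control risk is 0.9 × 12 × (0.75 × 0.03 + 0.25 × 0.01) = 0.270. The treated risk is 0.8 × 0.270 = 0.216. With 1,000 per arm, the two-proportion test gives 80.4%. Compounded risk with everyone at 3% per month gives 81.5%. Read instead as HR 0.80 with a log-rank test, power is at most about 71% at 10% immune. That shortfall comes from the effect scale, not from immunity, and is not part of this point.

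**Step 2: effect of the immune share alone.** Accept 80% at 10% protected. Log-rank power is Φ(|ln HR| × √(D/4) − 1.96), with events D proportional to 1 − f, where f is the effective share protected at entry. At 80% power the first term is 1.9600 + 0.8416 = 2.8016. Hence

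power(f) = Φ(2.8016 × √((1 − f)/0.9) − 1.96).

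| f | (1 − f)/0.9 | first term | power |
|---|---|---|---|
| 10% | 1.000 | 2.802 | 80% |
| 20% | 0.889 | 2.641 | 75% |
| 25% | 0.833 | 2.557 | 72% |
| 30% | 0.778 | 2.471 | 70% |
| 40% | 0.667 | 2.287 | 63% |
| 50% | 0.556 | 2.088 | 55% |

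On the same scale, the smallest reduction detectable with 80% power is 1 − exp(−0.2231 × √(0.9/(1 − f))): 20% at f = 10%, about 22% at 30% and about 26% at 50%. This ignores the slightly smaller event count under a larger effect.

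**Step 3: cross-check on the readings that reproduce 80%.** At f = 20%, 30% and 50%, the linear reading gives 74.2%, 67.0% and 50.1%; the compounded reading gives 75.3%, 68.1% and 51.1%. They fall somewhat faster than the table because a fixed 20% risk reduction corresponds to a weaker hazard ratio when risks are lower (0.773 at f = 10%, 0.787 at 50% in the linear reading).

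**Step 4: partial protection.** Take HR 0.80, 3% per month and nobody immune: about 560 events. If half the sample has its hazard halved, events fall to about 431, close to the 420 obtained at f = 25%. So 50% with antibodies or vaccination at half protection behaves roughly like f = 25%.

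**Step 5: dependence on incidence.** In the same model, f = 10% gives 504 events, 30% gives 392 and 50% gives 280. About 4.1% per month at f = 30%, or 6.3% at f = 50%, would restore the 504.

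**The case against.** The strongest reply is that this is an ageing planning assumption, not a miscalculation, and that the documents never show an entry share above 10%. That is right. The only baseline figure is the 10% antibody expectation in section III.

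A reader might infer from "it is likely that most participants have COVID-19 antibodies" that the sponsor itself expects most entrants to be immune. The documents do not support that. The sentence covers the course of the study and justifies dropping end-of-study tests; some of those antibodies would come from infections counted as outcome events. Section VIII also tells participants that antibodies are not known to indicate immunity. The point rests on eligibility, the immunized subgroup and the randomization window instead.

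Three further objections stand in part:

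- Immunity and incidence act together. Moving one to 2022–2024 levels while holding the other at 2020 values is artificial. The SAP says every participant could be active after Omicron arrived, while section XI mentions low reported COVID rates in 2021, so incidence could err either way.
- The 3% and 1% are given per person, not per susceptible person. If they are whole-population rates, some immune people are already in the denominator, and removing them again would double-count.
- Enrolment of people with known past infection is inferred from the absence of an exclusion; the documents do not report it.

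Finally, a null result is better judged by its confidence interval, and the SAP's significance rule does not use power. That limits the consequence but does not make the stated input correct.

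**Conclusion.** The point holds in limited form. The immunity input covers only one of three routes to protection at entry, and calling it conservative is not justified for later entrants. With the other inputs fixed and 80% accepted at 10% protected, power falls to about 75%, 72%, 70% and 55% at an effective 20%, 25%, 30% and 50% protected. These figures rest on assumed shares, full protection within each share, two-sided testing and unchanged incidence.

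A reader might go further and conclude that the trial's true power is some particular figure well below 80%. The documents do not support that: they give neither the protected share nor the later incidence, and a plausible change in incidence could cancel or deepen the loss. What they support is that the stated 80% describes a more susceptible population than the eligibility rules and randomization window allow, and should be given as a conditional range.

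**What to change.** In Protocol sections III and IX:

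1. Remove the description of the immunity input as conservative. Replace the input with the effective share protected at entry, counting vaccination, known past infection and unrecognised past infection.
2. Inform it with the baseline immunization status that the SAP's subgroup analysis requires. For early entrants, also use the baseline antibody subset; its kits were to be mailed within the first two quarters, so it cannot speak for 2022 to 2024.
3. Rerun the simulation jointly with the incidence input, for example from blinded pooled event rates. State the effect scale, the racial mix, and whether incidence is per person or per susceptible person.
4. Restate the power for a 20% reduction, or the smallest reduction detectable with 80% power, over 10% to 50% effectively protected.

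Leave the enrolment target unchanged. The cost is a wording change and a rerun of an existing simulation, with no effect on the analysis. The downside is that the stated power may become less favourable.

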## **X. Potential risks and benefits to subjects:**

*There are four minimal risks associated with the baseline survey and overall study participation.*

Confidentiality risk: There is a small chance that someone could find out that a subject is participating in this study or access the study data. However, we will take every precaution to protect subject privacy. In addition to using the Health Labs limiting data access to specified research staff, each person on the research team will be trained in human subject's protections and HIPAA policies and best practices. Additionally, we will minimize the risk of exposure or accidental disclosure to the fullest extent possible by maintaining all research data only on secure, password and firewall protected network computer accounts, limiting access to those data files to members of the research team, and only communicating data findings in the aggregate form. All names and other protected health information will be deleted from study records whenever possible. For example, in analytic datasets, participants will typically be identified by their unique study numbers.

Vitamin D toxicity risk: There is a very small chance that a participant could develop symptoms of vitamin D toxicity, including hypercalcemia, falls, hyperparathyroidism, or kidney stones. The health issues above are included in our exclusion criteria to further minimize this risk. Risk of toxicity could also be increased if patients take other vitamin D supplements, which they will be advised not to do. All patients will be informed about symptoms of vitamin D toxicity and advised to contact their physician if symptoms occur. The highest dose

administered as part of the study is considered by the National Academy of Medicine as low risk for the vast majority of the population without direct medical supervision,

Vitamin D insufficiency risk: There is a risk that some people in the 400 IU group may consume less than the daily RDA (600 IU) once diet (~200-300 IU/day) and the supplement are accounted for, but this risk is very low and reduced compared to not taking any vitamin D supplement. Persons whose doctors have advised higher doses will be excluded from the study.

Blood spot testing risk: The risks of a finger-prick required for blood spot testing are minor and include slight discomfort, the possibility of a bruise on the participant's fingertip and, rarely, infection or fainting. A small amount of blood may ooze from the fingertip, which can be easily stopped with gauze.

